Statistical Analysis Plan (SAP)

Study Title: Efficacy of Photobiomodulation Therapy Using 980nm Versus 635nm Diode Lasers in the Management of Myofascial Pain Syndrome (LLLT-MPS_sEMG)

ClinicalTrials.gov Identifier (NCT Number): NCT07069764

Document Date: 01 May 2025

Prepared by:

Principal Investigator: [name]

Institution: National Institute Enhanced of Laser Sciences

1. Introduction

This Statistical Analysis Plan (SAP) describes the pre-specified statistical methods and procedures that will be used to analyze data for the clinical trial entitled 'Efficacy of Photobiomodulation Therapy Using 980nm Versus 635nm Diode Lasers in the Management of Myofascial Pain Syndrome (LLLT-MPS_sEMG)'.

2. Study Objectives

Primary Objective: To evaluate the effectiveness of photobiomodulation therapy using diode lasers (980nm vs 635nm) in reducing myofascial pain.

Secondary Objectives: To assess improvements in mandibular function and muscle activity (measured using sEMG).

3. Outcome Measures

Primary Outcome: Change in pain intensity measured by the Visual Analog Scale (VAS) from baseline to post-treatment and follow-up.

Secondary Outcomes:

- Change in Maximum Mouth Opening (MMO) from baseline to post-treatment and follow-up.
- Change in Lateral and Protrusive Movements (LM, PM).
- Change in surface electromyography (sEMG) activity of masseter and temporalis muscles.

4. Statistical Methods

Normality of data distribution will be assessed using the Shapiro-Wilk test.

If data are not normally distributed, non-parametric tests will be applied.

Within-group comparisons across time points (baseline, post-treatment, follow-up) will be analyzed using the Friedman test, followed by post-hoc pairwise comparisons with Bonferroni correction if significant differences are detected.

Between-group comparisons will be conducted using the Mann-Whitney U test on change scores.

Significance will be set at $p < 0.05$.

5. Effect Size Calculations

Effect sizes will be calculated to quantify the magnitude of differences:

- Kendall's W for Friedman test results (within-group changes).
- Rank biserial correlation (r) for Mann-Whitney U test results (between-group comparisons).

6. Handling of Missing Data

If missing data occur, an intention-to-treat (ITT) approach will be applied. Sensitivity analyses may be conducted to evaluate the potential impact of missing data.

7. Interim Analyses

No interim analyses are planned for this study.

8. Software

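### The secondary between-group tests are each judged at an unadjusted 0.05; with ten such tests, the chance of at least one false wavelength difference is about 27% to 34%

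*SAP*

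**What the plan says.** - SAP section 4 sets a single significance level: "Significance will be set at $p < 0.05".
- For the comparison of the two lasers it says: "Between-group comparisons will be conducted using the Mann-Whitney U test on change scores". It names no visits and no adjustment.
- The one multiplicity correction belongs to the within-group Friedman analysis: "followed by post-hoc pairwise comparisons with Bonferroni correction if significant differences are detected".
- SAP section 3 lists the secondary outcomes. MMO has both post-baseline times: "Change in Maximum Mouth Opening (MMO) from baseline to post-treatment and follow-up". The other two bullets name no times: "Change in Lateral and Protrusive Movements (LM, PM" and "Change in surface electromyography (sEMG) activity of masseter and temporalis muscles".
- SAP section 2 treats jaw function and muscle activity as two parts of the secondary objective: "To assess improvements in mandibular function and muscle activity (measured using sEMG".
- Neither document gives a testing order, an alpha allocation, a rule making secondary tests depend on the primary result, or a statement that they are exploratory.

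**The concern.** The trial asks whether 980 nm and 635 nm differ. The SAP corrects for multiplicity in comparisons over time inside one arm, which cannot answer that question, and leaves the tests that can answer it uncorrected. Read as written, any single secondary Mann-Whitney p below 0.05 counts as a significant difference between wavelengths. With several outcomes and two post-baseline visits, such a result can easily arise by chance. The number of tests is not fixed either, so it could grow once the data are seen.

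**Working it through.** **Inputs**

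- Threshold 0.05 per test (SAP section 4). Sidedness is not stated; two-sided is assumed.
- 30 patients in two groups (Protocol, Patient assignment and blinding). The split is not stated; 15 per arm is assumed.
- Three time points for the within-group analysis (SAP section 4), hence two change scores per measure. Using both for the between-group tests is stated for MMO and inferred for the rest. The Protocol's Patient assessment section supports this for jaw movements, which are measured at every assessment.
- Correlations between change scores are not given. They are assumed and varied below.

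The documents state no error rate for this family, so there is no figure of theirs to reproduce.

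**Step 1. Count the tests**

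- Literal minimum: 2 for MMO + 1 each for LM, PM, masseter and temporalis = 6.
- Both visits for all: 5 measures × 2 = 10, of which 3 × 2 = 6 are function (MMO, LM, PM) and 2 × 2 = 4 are sEMG.
- The Protocol's Patient assessment section records mouth opening under two conditions and lateral movement to right and left. If all of these are tested: 7 measures × 2 = 14.

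**Step 2. Independent tests, no true difference**

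Chance of at least one false positive = 1 − (1 − α)^k.

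- α = 0.05: k = 6 gives 1 − 0.95^6 = 26.5%; k = 10 gives 1 − 0.95^10 = 40.1%; k = 14 gives 51.2%.
- The exact Mann-Whitney test at 15 v 15 rejects when U ≤ 64, a true size of 0.0453. Then k = 10 gives 1 − 0.9547^10 ≈ 37%, and k = 6 gives about 24%.

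**Step 3. Correlated tests, no true difference**

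These are simulated exact Mann-Whitney tests on normal change scores, 15 per arm. The correlation between two different outcomes at two different visits is the product of the outcome and visit correlations.

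| Visit correlation | Outcome correlation | 10 tests | 6 function tests |
|---|---|---|---|
| 0.7 | 0 | 34.0% | 21.3% |
| 0.7 | 0.3 | 30.8% | 20.7% |
| 0.7 | 0.5 | 27.8% | 20.0% |
| 0.8 | 0 | 31.4% | 20.0% |
| 0.8 | 0.3 | 29.8% | 19.9% |
| 0.8 | 0.5 | 26.4% | 18.0% |

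Each cell uses 10,000 replicates, so its standard error is at most about √(0.3 × 0.7 / 10,000) ≈ 0.5 points. A separate run over visit correlation 0.6 to 0.8 and outcome correlation 0 to 0.5 gave 26.5% to 34.4% for ten tests and 18% to 22% for six.

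Outside that grid:

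- Ten tests, one common correlation: 35.8% at 0.2, 27.5% at 0.5, 21.1% at 0.7, 17.7% at 0.8.
- Six function tests: down to 16.4% at visit correlation 0.8 and outcome correlation 0.7.
- Fourteen tests with correlation: about 27% to 46%.

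**Step 4. After adjustment**

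The first Holm step for ten tests is 0.05 / 10 = 0.005. With independent tests, 1 − 0.995^10 = 4.9%. Holm keeps the family rate at or below 5% under any correlation.

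**Step 5. Cost in power**

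For a true difference of 1 SD with 15 per arm, simulated Mann-Whitney power is about 72% at 0.05 and about 38% at 0.005.

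**The case against.** The sponsor can fairly reply that there is one primary outcome, that the rest are labelled secondary, and that reading unadjusted secondary tests as supportive is common in a 30-patient study. SAP section 5 also requires a rank-biserial effect size for between-group results, so the p-value would not stand alone. The secondary objective speaks of improvement, which the within-group analysis addresses with its own correction. All of this limits the weight of the point. It does not remove it, because the SAP nowhere says that secondary between-group results are supportive only.

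A reader might infer four stronger things that the documents do not support:

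- **That a false secondary finding is likely.** Every ten-test figure above is below one half.
- **That 27% to 34% is the risk of a false claim about jaw function.** Four of the ten tests are sEMG, which SAP section 2 separates from function. The function figure is about 16% to 26%.
- **That the SAP commits to at least ten tests.** Only MMO carries both visits explicitly, and the literal minimum is six. Nor do the documents say that sEMG is tested by side.
- **That the sponsor will announce a wavelength advantage from one small p-value.** No text says so; the text only fails to prevent it.

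**Conclusion.** The gap is real but modest: no multiplicity control and no exploratory label covers the secondary between-group tests. With ten tests, the chance of at least one false wavelength difference is about 27% to 34% for visit correlation 0.6 to 0.8 and outcome correlation 0 to 0.5. Across weaker and stronger correlations it is roughly 20% to 40%. For function alone it is about 16% to 26%. All these figures assume no true difference on any of the outcomes counted, two-sided tests, and the test counts in Step 1. The simulated ones also assume 15 per arm. Even the low end is more than three times the nominal 5%. The primary VAS comparison is not affected, so this should be corrected but does not threaten the main result.

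**What to change.** Add to SAP section 4, before any between-group analysis:

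1. A closed list of the secondary between-group tests: one chosen MMO condition, one rule for combining right and left lateral movement, PM, one sEMG summary for each muscle, and both post-baseline visits for each. Without this list the Holm denominator could be chosen after the data are seen.
2. A statement that unadjusted secondary p-values and rank-biserial effect sizes are descriptive.
3. A statement that no claim favouring either wavelength will be made from a secondary outcome unless its Holm-adjusted p across that list is below 0.05.

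If the sponsor wants no formal secondary claims, items 1 and 2 suffice, with the tests labelled exploratory.

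The change is wording only and needs no extra patients, visits or measurements. Its cost is the loss of power for a formal secondary claim shown in Step 5. That loss applies at the first Holm step; later steps are less strict.

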### Materials and methods

#### Patient assignment and blinding:

30 PATIENTS. Divided in to 2groups.

Comparison between two groups , First one, By using diode laser 635nm (flat top handpiece)

And other group by using diode laser 980nm (flat top handpiece).

The hand-pieces fixed at distances of 3 mm and 15 mm from the power meter, only the FT profile hand-piece had a constant power output, which was comparable to the contact mode.

Introsion criteria:-patients with Tmds due to stress,medically free, not to resort to self-medication during the study period.

Extrusion criteria:-patients with bruxisms, erosions,medically free,diabetics

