### Patient assessment:

The patients were evaluated before treatment ,after laser applications ,at the end of treatment , and 1 month after the laser applications.(18)

Evaluation of the patient is determined by pain intensity, maximum mouth opening(MMO), lateral movements(LM), protrusive movements(PM), pressure pain threshold, electromyography activity and TMJ sounds in patients with TMDS.(1,3,4,5)

At each assessment interval, the amount of mouth opening and the range of protrusive and lateral excursive movements of the jaw were measured and recorded. To measure mouth opening, the patient was asked to open the mouth at both "maximum pain-free" and "maximum possible" conditions.

The vertical interincisal distance was then measured with a digital caliper and recorded in millimeters in patient's folder.

The right and left lateral jaw movement was measured in millimeters by detecting the horizontal distance between the midpoints of the upper and lower central incisors.

A visual analog scale (VAS) was used for calculating pain grade right before our therapy. Patients were asked to describe the degree of discomfort/pain from zero to ten, the pain scale read "no pain" and "the greatest pain possible.

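### Kendall's W is the only within-group effect size in the SAP, but it shows neither the size nor the direction of change, and no effect is specified in VAS points or mm

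*SAP*

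**What the plan says.** SAP section 5 opens with its purpose: "Effect sizes will be calculated to quantify the magnitude of differences". It then names two measures. For change within an arm it is "Kendall's W for Friedman test results (within-group changes"; for the comparison of arms it is "Rank biserial correlation (r) for Mann-Whitney U test results (between-group comparisons".

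These accompany the tests in SAP section 4. Within each arm, "Within-group comparisons across time points (baseline, post-treatment, follow-up) will be analyzed using the Friedman test", with Bonferroni-corrected pairwise follow-up tests. Between arms, "Between-group comparisons will be conducted using the Mann-Whitney U test on change scores".

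The primary outcome in SAP section 3 is "Change in pain intensity measured by the Visual Analog Scale (VAS) from baseline to post-treatment and follow-up". The Protocol (Patient assessment) gives the pain scale: "Patients were asked to describe the degree of discomfort/pain from zero to ten". It records mouth opening and lateral jaw movement in millimetres.

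Neither document specifies a median or mean change, a difference in VAS points or millimetres, or a confidence interval for any of these.

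**The concern.** W is computed after each patient's scores have been replaced by ranks across the visits, so VAS points and millimetres are gone before the calculation starts. A statistic built this way cannot do what section 5 asks of it. It answers a different question: do patients agree on the order of the visits?

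Two things are at stake. First, the specified output is p-values plus two unitless rank statistics. From those alone a reader could not learn how much pain fell in either arm, although reducing pain is the primary objective. Second, each arm will have its own W, described as a magnitude. Anyone who sets the two side by side may draw the wrong conclusion about which laser relieved more pain.

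**Working it through.** The documents give no value of W, no SD and no expected change, so there is no planned figure to reproduce. The check is whether W responds to the size of change at this trial's dimensions.

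**Inputs from the documents.** k = 3 time points (SAP section 4); a 0 to 10 pain scale (Protocol, Patient assessment); "30 PATIENTS. Divided in to 2groups" (Protocol, Patient assignment and blinding).

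**Assumptions.** n = 15 per arm, because no allocation ratio is stated. All VAS values and SDs below are also assumed.

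**Formula (no ties).** W = 12S / [n²(k³ − k)], where S is the sum of squared deviations of the visit rank sums from their mean. With n = 15 and k = 3 the mean rank sum is 30 and the denominator is 225 × 24 = 5400.

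**1. Size.** Every patient falls by the same amount at each step. Rank sums are 45, 30, 15, so S = 15² + 0 + 15² = 450 and W = 5400/5400 = 1.00. The result is the same for steps of 0.1, 1 or 3 points.

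**2. Direction.** Every patient worsens 3 → 5 → 7. Rank sums are 15, 30, 45, S is again 450 and W = 1.00.

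**3. Early relief that is held.** Every patient drops about 5 points, but the two later visits differ by 0.1, in one order for 8 patients and the other for 7. Rank sums are 45, 22, 23, so S = 225 + 64 + 49 = 338 and W = 4056/5400 = 0.75. This is below the W for a uniform 0.1-point fall.

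More generally, suppose every patient is better at both later visits and the order of those two visits is a coin toss. The later rank sums are 22.5 ± d, with d² averaging 15/4 = 3.75. Expected S is 225 + 2(7.5²) + 2(3.75) = 345, and expected W = 4140/5400 = 0.77, however large the relief. If the two later scores tie exactly in everyone, the tie-corrected W is 1.00.

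**4. Two constructed arms.** Arm A: all 15 patients go 7.0 → 6.8 → 6.6. Arm B: 11 go 7 → 3 → 2, two go 7 → 2 → 3, and two go 7 → 7.5 → 8.
- A: W = 1.00, mean relief at follow-up 0.4.
- B: rank sums 41, 28, 21, S = 121 + 4 + 81 = 206, W = 2472/5400 = 0.46. Mean relief at follow-up is (11 × 5 + 2 × 4 − 2 × 1)/15 = 4.07.
- Rank biserial r on change at follow-up: (13 × 15 − 2 × 15)/225 = 0.73 in favour of B. So r has the direction right and W does not.

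**5. Simulation with noise.** Baseline mean 7, between-patient SD 1.5, independent visit noise as shown, 3,000 runs per scenario. Falls are from baseline to post-treatment / follow-up. A run counts as reversed when the arm with less true relief has the higher W although observed mean relief at follow-up is in the true order.

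| Lesser-relief arm | Greater-relief arm | Mean W, lesser vs greater | Reversed |
|---|---|---|---|
| 2 / 4, SD 1.0 | 5 / 5, SD 1.0 | 0.86 vs 0.77 | 81% |
| 0.5 / 1.0, SD 0.2 | 3 / 3, SD 1.5 | 0.93 vs 0.57 | 99.7% |
| 1.5 / 2.5, SD 1.0 | 3 / 3, SD 1.0 | 0.63 vs 0.72 | 18% |
| 1 / 1.5, SD 1.0 | 3 / 3, SD 1.0 | 0.36 vs 0.72 | 2% |

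**6. Same noise, same shape.** With SD 1.5 and a steady decline of 1, 2 or 3 points per visit, mean W is about 0.31, 0.66 and 0.85. Here W does rise with relief.

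**The case against.** W is the customary companion to the Friedman test, and naming it is not an arithmetic mistake. The sentence about magnitude is a general lead-in to both measures. The SAP gives W no part in comparing the arms: that is done by Mann-Whitney on change scores with r, neither of which depends on W. The SAP is silent on descriptive summaries rather than excluding them. A uniform 0.1-point fall in 15 self-rating patients is also not a realistic data set. All of this is fair, and it limits the point to effect reporting.

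A reader might go further and infer that W tends to fall as pain relief grows, or that the plan will rank the lasers by W. The documents support neither. One can make W fall from 0.86 to 0.66 to 0.49 as the drop per visit goes from 1 to 2 to 3 points, but only by letting the assumed noise SD rise from 0.5 to 1.5 to 3. The drop divided by the SD then goes 2.0, 1.33, 1.0, so any standardised effect size would decline as well. Step 6 shows the opposite pattern when noise is held fixed.

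Two things survive. W lacks the property section 5 ascribes to it, which follows from its definition without any assumption about data. And wrong ordering does not need unequal noise: a different time profile is enough, as the first row of the table shows. An arm that gains early and holds its gain to follow-up is a plausible profile here.

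**Conclusion.** The point holds as a defect in how effects are reported. Section 5 assigns a measure of rank consistency to the task of showing magnitude, and nothing else in the SAP supplies an effect in VAS points or millimetres. Rank biserial r shares the lack of units, though it is computed on change scores and keeps the direction between arms.

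No test, error rate or planned between-arm conclusion is affected. Misordering of the arms by W is possible rather than expected: it ran from 2% to 99.7% across the assumed scenarios, and it matters only if someone compares the two W values. The results in steps 1 and 2 are exact for any data with those patterns. The simulated figures rest on 15 patients per arm and on assumed falls and SDs, and exact ties between visits would change them.

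**What to change.** Amend SAP section 5 as follows.

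- Make the within-arm effect estimate the median (or mean, chosen in advance) change from baseline in each arm at post-treatment and at follow-up, with a 95% CI.
- Make the between-arm effect estimate the difference in change at each of those time points, with a 95% CI. The Hodges-Lehmann estimate pairs naturally with the planned Mann-Whitney test.
- Report these in VAS points for pain, millimetres for mouth opening and jaw movements, and the recorded unit for sEMG.
- If W is kept, describe it as consistency of rank order across visits, not as magnitude, and state that it is not compared between arms. Rank biserial r can stay as a supplement.

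The tests in section 4 stay as they are and no new data are needed, because the change scores are already computed for the Mann-Whitney test. The cost is a few lines of SAP wording and a few more lines of output.
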